6.0 Adverse event reporting

Adverse events (AEs) will be reported according to IRB policies and procedures. Reporting will depend on adverse event severity:

Grading of Severity

0. No AE or within normal limits.
1. Mild AE.
2. Moderate AE.
3. Severe AE resulting in inpatient hospitalization, or a persistent or significant disability/incapacity.
4. Life-threatening or disabling AE.
5. Fatal AE.

AE's of grade three or higher will be reported immediately to the IRB using the Report of Adverse Events per IRB policies and procedures. Every six months the PI will summarize any AE's to the IRB. In conjunction with the IRB, the PI will determine if modifications to the protocol are warranted.

Serious and unexpected adverse events will be reported to our IRB within seven calendar days. All our adverse events will be reported as required at the time of continuing review. Protocol deviations and violations will be reported to our IRB within ten working days.

7.0 Study withdrawal/discontinuation

Subjects will be withdrawn from the study if they will not lie still in the scanner during data collection. In addition, subjects can voluntarily withdraw from the study at any time.

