approximately 90minutes. Patients undergoing 2-year monitoring will also undergo these non-MRI measurements at baseline, and every 5-7 months (targeting at 6months) up to 5 total visits within 2 years; and for this same group an MRI will be done at Visit 1 and then as needed based on symptoms, clinical therapies provided increasing risk of lymphedema such as radiation, and non-MRI measures at subsequent follow-up visits within the 2 year time period. For these follow-up visits non-involving MRI, the visits last approximately 30 minutes.

Perometer

L-Dex

LymphaTouch

MoistureMeter D/LymphaScanner

InBODY 770 (Body Composition)

SkinFibroMeter

5. For subjects enrolled in Aim 3 of this study, they will receive the above mentioned non-MRI and MRI measures (#2) at Visits 1, 11, 12 and 22. In addition the MLD screening form will be completed on Visit 1 in preparation for this component of their CDT during subsequent treatment visits, as well as completion of the Functional Outcome Measures (PSFS and UEFI) patient self-reports will be done on Visits 1, 11, 12 and 22 to establish baseline functional level and monitor during treatments. Then they will receive their assigned therapy intervention (CDT alone or CDT with graded negative pressure) at Visits 2-10 and 13-21. For Group 1, the first course of treatment will be CDT alone, then the second course of treatment will be CDT with graded negative pressure. For Group 2, the first course of treatment will be CDT alone, then the second course of treatment will be CDT with graded negative pressure. During all courses of treatment, it will consist of 9 visits within 6-8 weeks at 75minutes duration each visit, twice per week for three weeks and then once per week for 3-5 weeks. There will be a 4-8 week washout period between Visit 11 and Visit 12.
6. For the subgroup of subjects enrolled in the 1 time hourly treatment visit of Aim 3, they will receive the above mentioned MRI and nonMRI measures before and immediately following the 1x hourly treatment. The PSFS and UEFI questionnaires will not be administered for this 1x treatment visit only. The participants will undergo (i.) CDT alone, (ii.) CDT with graded negative pressure, or (iii.) exercise and self management treatment. This subgroup participation may involve undergoing all three of the single treatment options on different study dates if the participant is interested otherwise the study only only involves this one-time study visit.

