8.0 Statistical analysis plan

Statistical analysis will be overseen by statistician co-investigators. Means, standard deviations, and ranges for continuous variables will be recorded, along with tests for normality and homoscedasticity. The primary statistical objective is to assess whether the changes, pre- vs. post-intervention, in internal imaging metrics of lymphatic clearance or PSFS score are different for the standard CDT therapy or CDT therapy with negative pressure. First, a Student's t-test or Wilcoxon signed-rank test (depending on normality results) will be applied to test the difference between each measurement for the same subject for each of the two therapy sessions. We will also test the difference of any potential carryover effect and we will apply a general linear model approach, in which we include the treatment and treatment-period interaction in the model. Power calculations are based on our preliminary data that observed an improvement in PSFS in five patients on CDT with negative pressure vs. CDT alone, as well as an ability to detect a mean change in T_2 and lymphangiography score pre- vs. post-MLD of N. With the premise that CDT with negative pressure will be at least as good as CDT without negative pressure, with the proposed sample size, we will have 80% power to detect a 40% reduction rate with one-sided type I error = 5%.

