10.0 Follow-up

No specific follow-up scans are required for Aim 1 unless patients are eligible and would like to enroll in the 2-year monitoring aim of the study (Aim2). For Aim 2, subjects will be able to contact the PI and co-investigators with any questions and a KSP will contact them to schedule their 6-8 month follow up visits for a total of 4 within the 2 year monitoring period. For Aim 3, subjects will be scheduled for all treatment visits prior to start of each course of treatment (Visits 2-10 and 13-21). The subjects will be able to contact the KSP with any questions and needs to change their assigned treatment times and dates should any adjustments be necessary. The subjects will be contacted during their washout period to schedule their second course of treatment visits and intake and exit measurement visits. An unwillingness to participate in any future scans or treatments will not influence or disqualify a volunteer from participating in the first instance. For the one-time treatment subgroup of Aim 3, this is a one-time visit for the pre and post MRI and nonMRI measures with no further study follow-up unless the participant wishes to undergo all three separate treatment interventions at different dates for interperson treatment comparison. For participants in Aim 2 (monitoring period), if the lymphedema specialist recommends lymphedema management, then the subject will be encouraged to seek out clinical care which does not prevent them from being able to participate in this study, including patients being monitored over 2-years. The lymphedema specialist will help the client obtain orders and location of treatment if subject would like assistance.

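### Section 7.0 withdraws a subject from the whole study over a failed scan, so a failure after Visit 1 ends later PSFS and other outcomes that need no scan

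*Combined protocol and SAP*

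**What the plan says.** **The rule.** Section 7.0 has two sentences. The first is "Subjects will be withdrawn from the study if they will not lie still in the scanner during data collection". The second allows voluntary withdrawal at any time. Neither is limited to the MRI component or to one aim, and neither says what happens to data already collected or to measurements still due.

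**The nearest softening text.** Section 10.0 says: "An unwillingness to participate in any future scans or treatments will not influence or disqualify a volunteer from participating in the first instance". This is about being allowed to enter. It does not address a subject already in the study whose scan fails.

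**Aim 3 outcomes.** Section 8.0 frames the primary objective as a comparison of changes "in internal imaging metrics of lymphatic clearance or PSFS score" between the two therapies. Section 5.0, item 5, schedules PSFS and UEFI as follows: "patient self-reports will be done on Visits 1, 11, 12 and 22". The MRI and external measures fall on the same four visits. The first planned analysis is to "test the difference between each measurement for the same subject for each of the two therapy sessions", after which "we will apply a general linear model approach, in which we include the treatment and treatment-period interaction in the model".

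**Aim 2 outcomes.** Section 5.0, item 4, schedules non-MRI measures at baseline and then "every 5-7 months (targeting at 6months) up to 5 total visits within 2 years". MRI is done at Visit 1 and afterwards only as needed. Visits without a scan are already part of the plan: "For these follow-up visits non-involving MRI, the visits last approximately 30 minutes".

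**The concern.** PSFS and UEFI are questionnaires, and the external measures (Perometer, SkinFibroMeter, InBODY 770, L-Dex, MoistureMeterD/LymphScanner) are taken outside the magnet. Movement in the scanner spoils the image but does not prevent any of these from being obtained. A rule that removes the subject from the study gives up outcomes that could still be collected, one of them named in the primary objective.

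In the cross-over the first planned test is within-subject, so a subject who has the first course but not the second contributes no complete comparison to it. By Visit 11 such a subject has been scheduled for nine treatment visits. In Aim 2 the same rule ends follow-up visits that the plan would otherwise run with no scan at all.

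**Working it through.** **1. Scope of the rule.** Set side by side, section 7.0 withdraws the subject from the study, section 10.0 deals with entry only, and section 8.0 states no handling of missing data or of withdrawn subjects. That later non-MRI collection ends is an inference from the wording of section 7.0 and the absence of any provision to continue. It is the plain reading, but the documents do not state it in terms.

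**2. Aim 3 cross-over: PSFS values lost.** PSFS is due at Visits 1, 11, 12 and 22 (4 values). Values lost = scheduled values after the visit of withdrawal, plus 1 if PSFS is completed after the scan at that visit. The documents do not give the order of PSFS and scan, so both cases are shown. UEFI has the same schedule and the same counts.

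| Failed scan at | PSFS before scan | PSFS after scan | Two-course comparison |
|---|---|---|---|
| Visit 11 | 2 lost (Visits 12, 22) | 3 lost (11, 12, 22) | Not available |
| Visit 12 | 1 lost (22) | 2 lost (12, 22) | Not available |
| Visit 22 | 0 lost | 1 lost (22) | Available only if PSFS came first |

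The comparison needs two changes: Visit 11 minus Visit 1, and Visit 22 minus Visit 12. A failure at Visit 12 leaves the first change intact. So does a failure at Visit 11 if PSFS came before the scan. The general linear model might use that single-course change; section 8.0 does not say.

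For the external measures, section 5.0, item 4, places them before the MRI, so only later visits are lost: 2, 1 and 0 sets for a failure at Visit 11, 12 and 22.

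**3. Aim 2: non-MRI visits lost.** With up to 5 visits in total, and external measures before the scan, later visits lost = 5 − (number of the visit with the failed scan):

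- Visit 2: 5 − 2 = up to 3
- Visit 3: 5 − 3 = up to 2
- Visit 4: 5 − 4 = up to 1
- Visit 5: 5 − 5 = 0

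**4. Visit 1 kept apart.** In Aim 3 the Visit 1 scan comes before any therapy (Visits 2-10 are the first course). In Aim 2 a subject without a usable Visit 1 scan has no baseline imaging marker, so later visits could not serve Hypothesis 2, which compares imaging markers with established risk factors. Counting those visits as lost would inflate the harm.

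**5. Parts of the study where little is at stake.** The one-time treatment subgroup of Aim 3 does not complete PSFS or UEFI (section 5.0, item 6), and Aim 1 requires no follow-up scans (section 10.0).

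**6. The plan's own power figure.** Section 8.0 states 80% power for a 40% reduction rate at one-sided 5%. It cannot be reproduced: the text gives no sample size, standard deviation, baseline rate or attrition allowance, and does not tie the 40% to a paired PSFS comparison. A change in power from withdrawals therefore cannot be derived.

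**The case against.** The best defence is that this is an MRI study and the rule fits it. Section 3.0 excludes MRI contraindications, severe claustrophobia, noticeable anxiety and severe vertigo in the magnet, and subjects who cannot adhere to the protocol. Withdrawing someone who will not keep still is consistent with those criteria, and the exclusions should make the event uncommon, especially in subjects who have already completed a scan. This stands as a limit on size. At Visit 1 it largely answers the point. It does not explain why PSFS or arm measurements should stop after a usable first scan.

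A second objection is that the remedy may recover little: a two-course PSFS comparison exists only where both courses are received. That also stands. Where they are not, the gain is single PSFS, UEFI and external-measure values.

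A reader might infer three stronger things that the documents do not support:

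- **That Visit 1 failures are the largest loss**, because most scheduled values follow them. They resemble screen failures, for the reasons in step 4 of the working.
- **That power falls by a definite amount.** Any such figure would need an assumed loss rate, an assumed paired PSFS basis for the 80%, and a sample size that the text does not give.
- **That Aim 2 is biased in a known direction**, because later scans are prompted partly by symptoms, therapies or non-MRI findings. Exposure to the rule may depend on clinical course, but nothing in the text fixes a direction.

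**Conclusion.** The point holds for scan failures after a usable Visit 1 scan. Its core is Visits 11 and 12 of the Aim 3 cross-over, where the later non-MRI outcomes end and no two-course PSFS comparison remains. Visit 22 matters only if PSFS is completed after the scan. In Aim 2 the loss is confined to failures at later as-needed scans.

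The conclusion rests on reading withdrawal from the study as ending all later collection. If staff already apply the rule only to the scan, the change simply brings the text into line with practice. The overall effect is probably small and cannot be quantified from the documents. This is a worthwhile inexpensive improvement and does not call the validity of the design into question.

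**What to change.** In section 7.0, limit the rule to the MRI component for subjects who already have a usable Visit 1 scan. Suggested text:

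> If a subject will not lie still at a later scan, that scan is recorded as missing. Data already collected are kept. PSFS, UEFI and non-MRI measures continue to be collected at the remaining scheduled measurement visits, and all available non-MRI data are analysed, with the treatment course actually received recorded.

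Leave the sentence on voluntary withdrawal as it is. Whether study therapy continues after a failed scan is for the investigators to state separately; no rule on it is proposed here.

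The cost is a short rewording, with no new visits or procedures. The downside is that some subjects will have non-MRI outcomes without a matching MRI.

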8.0 Statistical analysis plan

Statistical analysis will be overseen by statistician co-investigators. Means, standard deviations, and ranges for continuous variables will be recorded, along with tests for normality and homoscedasticity. The primary statistical objective is to assess whether the changes, pre- vs. post-intervention, in internal imaging metrics of lymphatic clearance or PSFS score are different for the standard CDT therapy or CDT therapy with negative pressure. First, a Student's t-test or Wilcoxon signed-rank test (depending on normality results) will be applied to test the difference between each measurement for the same subject for each of the two therapy sessions. We will also test the difference of any potential carryover effect and we will apply a general linear model approach, in which we include the treatment and treatment-period interaction in the model. Power calculations are based on our preliminary data that observed an improvement in PSFS in five patients on CDT with negative pressure vs. CDT alone, as well as an ability to detect a mean change in T_2 and lymphangiography score pre- vs. post-MLD of N. With the premise that CDT with negative pressure will be at least as good as CDT without negative pressure, with the proposed sample size, we will have 80% power to detect a 40% reduction rate with one-sided type I error = 5%.

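### Section 8.0 frames Aim 3 as a comparison of pre-to-post changes and names no baseline covariate, giving up precision that the Visit 1 and Visit 12 measurements could supply

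*Combined protocol and SAP*

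**What the plan says.** Section 8.0 states the primary objective as to "assess whether the changes, pre- vs. post-intervention, in internal imaging metrics of lymphatic clearance or PSFS score are different" between CDT and CDT with negative pressure. For the first analysis, "a Student's t-test or Wilcoxon signed-rank test (depending on normality results) will be applied" to within-woman differences between the two courses. A general linear model follows, "in which we include the treatment and treatment-period interaction in the model". The response of that model is not defined, and no baseline term is mentioned anywhere in the section.

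Section 5.0, item 5, gives the measurement times. Aim 3 participants have "non-MRI and MRI measures (#2) at Visits 1, 11, 12 and 22". For PSFS and UEFI, "patient self-reports will be done on Visits 1, 11, 12 and 22 to establish baseline functional level". Treatment runs over Visits 2-10 and 13-21, so each course has its own baseline (Visit 1 or 12) and its own exit value (Visit 11 or 22). On the gap between courses, the same item says: "There will be a 4-8 week washout period between Visit 11 and Visit 12".

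**The concern.** In a parallel-group trial, subtracting baseline removes stable differences between people. In a cross-over the within-woman comparison has already removed them. What the subtraction then brings in is the visit-to-visit variation of two further measurements, each given a fixed weight of one however well it predicts the exit value. Adjustment lets the data set that weight.

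At stake is the precision of the primary comparison, for imaging and PSFS alike, in a trial that asks each woman for 22 visits and four MRI sessions. The covariates are already being collected.

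**Working it through.** **1. The plan's own figure.** Section 8.0 claims 80% power at one-sided 5% for a 40% reduction rate. This can be neither reproduced nor refuted, because the sample size, the SD and the endpoint or scale of that rate are not given. For a paired contrast, N = ((1.645 + 0.842)/d)² = 6.18/d². That is 69, 25 or 10 women for an assumed standardized effect d of 0.3, 0.5 or 0.8. Only relative precision can be examined from here on.

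**2. Variance of the two contrasts.** Inputs: four measurements per woman (Section 5.0, item 5). Assumptions: equal variance at the four visits and no carryover. Let dE be her exit value in one course minus the other, and dB the same difference for baselines. Each has variance V, and their correlation is r.

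- Change score: Var(dE − dB) = 2V(1 − r).
- Baseline-adjusted: residual Var(dE given dB) = V(1 − r²).
- Ratio, change over adjusted: 2(1 − r)/(1 − r²) = 2/(1 + r).

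This gives 2.00 at r=0, 1.54 at r=0.3, 1.33 at r=0.5 and 1.18 at r=0.7. Against the exit difference alone (variance V), subtraction adds noise only when r is below 0.5. Against the adjusted contrast it is never better in large samples.

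**3. Plausible r.** The documents give no correlations, so these are assumed structures.

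| Structure | Ratio |
|---|---|
| All four visits equally correlated (r=0) | 2.00 |
| Within-course / between-course correlation 0.6/0.5, where r = (0.6 − 0.5)/(1 − 0.5) = 0.2 | 1.67 |
| 0.8/0.7 | 1.50 |
| 0.9/0.8 | 1.33 |
| 0.9/0.5 | 1.11 |
| Serial correlation, weeks 0, 7, 13, 20 | 1.43 to 1.86 |
| Serial correlation, weeks 0, 7, 33, 40 (washout in months) | 1.1 to 1.6 |

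**4. Meaning for power.** Suppose, as a yardstick only, that the change-score test has 80% power. Adjusted power is then Φ(2.486·√ratio − 1.645): 96.9% at r=0, 92.5% at r=0.3, 89.0% at r=0.5 and 85.4% at r=0.7. If instead the adjusted test has 80%, the change score has 54.5% at r=0 and 69.4% at r=0.5.

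**5. Small samples.** Simulation with two treatment orders and 4,000 runs, charging the degree of freedom for the covariate. The sample sizes are assumed.

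| Women | r=0: variance ratio; power, change vs adjusted | r=0.5: variance ratio; power, change vs adjusted |
|---|---|---|
| 10 | 1.67; 75% vs 90% | 1.17; 73% vs 78% |
| 20 | 1.83; 78% vs 95% | 1.23; 77% vs 85% |
| 40 | 1.87; 79% vs 96% | 1.33; 79% vs 87% |

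**6. Carryover.** Let δ be the treatment effect, λ the difference at Visit 12 due to which therapy came first, and f the fraction of λ still present at Visit 22. With two orders, half the between-order contrast in dE has expectation δ − fλ/2, and in dB −λ/2. Hence:

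- change score: δ + (1 − f)λ/2
- adjusted (slope r): δ − (f − r)λ/2

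Take δ=0.5 SD, λ=0.3 SD and r=0. Carryover that fully persists (f=1) gives 0.50 for the change score and 0.50 − 0.15 = 0.35 adjusted. Carryover that has gone by Visit 22 (f=0) gives 0.65 and 0.50. The adjusted estimate has the smaller bias when f is below (1 + r)/2.

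**The case against.** The strongest objection is that Visit 12 is not a pre-treatment covariate, since it follows the first course. If that course leaves a lasting effect that differs by therapy, the change score cancels it and adjustment does not. In a simulation with 24 women, all correlations 0.7, an effect of 0.5 SD and 4,000 runs, adjustment raised power from 70% to 91% without carryover. With persistent differential carryover of 0.3 SD the gain vanished (68% for change, 66% for adjusted). Section 1.0 describes these therapies as disease-modifying, so lasting effects are plausible. This stands, and it is the reason to keep the change score. It does not make the change score the better primary analysis, because carryover that fades by Visit 22 biases the change score instead.

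Second, the wording of Section 8.0 is loose. The sentence on the paired test is ambiguous, and the model's terms are listed without saying that they are the only ones. That raw changes are used throughout is an inference from the stated objective and from the absence of any baseline term. That also stands. The remedy is to state the response and the covariates.

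Third, Section 5.0, item 5, gives Groups 1 and 2 the same order of therapies. As written, sequence is constant and treatment is confounded with period, so a sequence term cannot be estimated. This is a separate fault that affects either analysis, but the fix below depends on resolving it.

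Fourth, a single parametric model would lose the non-normal route that the Wilcoxon test provides. That is met by specifying a rank-based or permutation version.

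**Conclusion.** The point holds as a matter of efficiency. On the stated objective, Section 8.0 compares changes and names no baseline adjustment, although both course baselines are measured. With equal visit variances and no carryover, the cost is a variance 2/(1 + r) times that of the adjusted contrast. In the structures tried with r above 0, the ratio is about 1.1 to 1.9.

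Three stronger readings should be resisted.

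- A reader might infer that the plan doubles the variance, or needs twice the women. Doubling is the r=0 case, and r is not in the documents.
- A reader might infer that the trial's 80% power would rise to about 97%. The stated 80% is attached to a reduction rate with no endpoint, scale, SD or sample size, so it cannot be tied to the change-score test or to any other.
- A reader might infer that change scores are invalid and should be dropped. With two orders and no differential carryover the comparison is unbiased, and under persistent carryover it is the less biased of the two.

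**What to change.** In Section 8.0, define the primary Aim 3 analysis, for imaging and PSFS alike, as a model of the exit values (Visits 11 and 22) with:

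- treatment, period, sequence and a random woman effect;
- the woman's mean course baseline (Visits 1 and 12) and her within-woman deviation from it as covariates.

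An equivalent form regresses the exit difference on sequence and the baseline difference. Specify a rank-based or permutation version for non-normal outcomes.

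Keep the change-score comparison as a pre-specified sensitivity analysis. State why: persistent differential carryover biases the adjusted estimate, and carryover that decays by Visit 22 biases the change score.

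Before the sequence and period terms can be fitted and interpreted, reconcile two places in Section 5.0. The orders for Groups 1 and 2 in item 5 are identical as written. The washout is 4-8 weeks in item 5 but 4-8 months in the compensation list (item 9).

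The cost is SAP wording, one or two degrees of freedom, and the dependence on carryover described above. No visit or measurement is added.

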Aim 1: Prevention. We will apply new anatomical and functional LN imaging approaches to identify LN profiles specific to biopsy-confirmed metastatic LNs; findings could be used to better inform LN removal and reduce the incidence of benign LN dissection. We will incorporate healthy female controls to serve as a comparison to the patient population.

Aim 2: Progression. We will improve our understanding of secondary lymphedema risk progression following cancer therapy by testing the hypothesis that superficial tissue profiles and subcutaneous adipose accumulation are more prevalent in patients experiencing lymphedema progression, and thereby could be used to triage patients for aggressive therapies prior to overt symptoms and irreversible damage.

Aim 3: Therapy. We will perform a repeated-measures cross-over trial to test the hypothesis that mobilization of protein enriched hardened tissue using graded negative pressure therapy in conjunction with complete decongestive therapy (CDT) is more effective to standard CDT alone for secondary lymphedema management. Both of these conservative physical therapy treatments are commonly employed for treatment of secondary lymphedema and the Vanderbilt Lymphedema Clinic utilizes the graded negative pressure therapy as a component of treatment. Additionally we will perform a subgroup of 1-time only hour treatment with before and after MRI and nonMRI measurements for additional immediate treatment impact in CDT, CDT with graded negative pressure, or exercise and self management treatment strategies alone as commonly performed in outpatient physical therapy clinics and at home for the management of BCRL.

The overarching goal is to develop objective markers of lymphatic dysfunction that can be used in emerging therapeutic trials of cancer and lymphedema therapies to be used to reduce both the incidence and severity of symptoms associated with this prevalent and chronic condition.

Aim (1). To compare *in vivo* anatomical and novel molecular imaging contrasts between LNs with versus without biopsy-confirmed metastasis.

Hypothesis (1). Biochemical LN profiles quantified from noninvasive chemical exchange saturation transfer (CEST) MRI provide discriminatory potential for distinguishing metastatic versus benign LNs pre-operatively. These biochemical profiles are more discriminatory than anatomical measures of LN morphology.

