Aim (2). To identify sub-clinical biomarkers of lymphatic insufficiency using quantitative evaluation of lymphatic vessel anatomy, axillary edema, and interstitial adiposity.

Hypothesis (2). Sub-acute internal imaging markers reflective of tissue microenvironment and interstitial adipose accumulation provide superior discriminatory abilities for portending BCRL progression compared with established risk factors such as BMI, age, and quantity of LNs removed.

Aim (3). To evaluate the impact of CDT with and without graded negative pressure therapy on internal measures of lymphatic dysfunction and edema in patients with chronic BCRL.

Hypothesis (3). Mobilization of protein-enriched hardened tissue using graded negative pressure therapy in conjunction with CDT will reduce (i) superficial markers of interstitial protein accumulation and (ii) lymph stasis, and improve (iii) patient-valued functional outcomes compared to standard CDT and/or exercise and self management treatment strategies.

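### Aim 3's primary objective joins several outcomes by *or* with no primary endpoint, success rule or alpha control, so the stated one-sided 5% is not held if any single win counts

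*Combined protocol and SAP*

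**What the plan says.** Section 8.0 (Statistical analysis plan) states one primary objective for the therapy comparison: whether the pre-to-post changes "in internal imaging metrics of lymphatic clearance or PSFS score are different for the standard CDT therapy or CDT therapy with negative pressure". The imaging metrics are plural and are not listed in that sentence. A t-test or Wilcoxon signed-rank test is then used to "test the difference between each measurement for the same subject for each of the two therapy sessions". T2 and a lymphangiography score are named in the same section, but only beside PSFS as the preliminary basis for the power calculation, not as endpoints.

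The power sentence reads "we will have 80% power to detect a 40% reduction rate with one-sided type I error = 5" per cent. It follows a premise that adding negative pressure is no worse than CDT alone.

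Elsewhere:

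- Section 2.0, Aim 3, is directional: the combination "is more effective to standard CDT alone for secondary lymphedema management".
- Section 2.0, Hypothesis 3, lists three unranked outcomes: the combination "will reduce (i) superficial markers of interstitial protein accumulation and (ii) lymph stasis, and improve (iii) patient-valued functional outcomes".
- Section 5.0, item 5, schedules "completion of the Functional Outcome Measures (PSFS and UEFI) patient self-reports" at Visits 1, 11, 12 and 22. UEFI is not mentioned in Section 8.0.

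**The concern.** A primary objective with a stated type I error needs a rule for what counts as meeting it. Here the objective spans several outcomes, each is tested, and nothing says whether one success is enough, whether all are needed, or which outcome leads. Under the permissive reading, the investigators could report whichever outcome reached significance as the primary result, and the 5% would not describe the risk of a false claim.

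Two further gaps prevent the reader from settling this. The objective asks whether the changes are *different*, the test sentence gives no sidedness, and one-sided 5% appears only with the power. The effect to be detected is a 40% reduction rate with no endpoint, scale or reference value, although the planned test compares paired changes.

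Section 1.0 (significance item 3) intends the findings to support wider healthcare coverage of these therapies, so the success rule should be fixed before the data are seen.

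**Working it through.** **Inputs.** From Section 8.0: alpha 5% one-sided, power 80%, a paired test on each measurement. Assumed, because the plan does not fix them: k = 2 outcomes (one MRI metric and PSFS) or k = 3 (one per outcome in Hypothesis 3), and a common correlation of 0, 0.5 or 0.8 between the test statistics. All calculations use normal test statistics.

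**The plan's own figure.** The 80% cannot be reproduced. The supplied text gives no numeric sample size, SD or baseline rate, and no scale for the 40%. At one-sided 5% and 80% power, different readings of the phrase require very different numbers:

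- Paired mean reduction of 40% of a reference mean, SD of the paired difference 0.4 to 1.2 times that mean: 8 to 58 subjects.
- Two independent proportions, 40% relative reduction from a rate of 50% to 100%: 74 down to 12 per group.
- Two independent proportions, 40-point absolute reduction from a rate of 40% to 90%: 12 to 19 per group.

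**If any one success counts, one-sided 5% tests.** With independent outcomes, P(at least one false claim favouring negative pressure) = 1 − 0.95^k:

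- k = 2: 1 − 0.95² = 0.0975
- k = 3: 1 − 0.95³ = 0.1426

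For correlated outcomes the same probability comes from numerical integration over equicorrelated normals with cut-off 1.645.

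| Outcomes | corr. 0 | corr. 0.5 | corr. 0.8 |
|---|---|---|---|
| 2 | 9.75% | 8.8% | 7.5% |
| 3 | 14.3% | 11.8% | 9.3% |

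**The same reading with two-sided 5% tests** (cut-off 1.960). For independent outcomes the favourable direction gives 1 − 0.975² = 0.0494 and 1 − 0.975³ = 0.0731.

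| Outcomes | Error counted | corr. 0 | corr. 0.5 | corr. 0.8 |
|---|---|---|---|---|
| 2 | favouring negative pressure | 4.9% | 4.5% | 3.9% |
| 3 | favouring negative pressure | 7.3% | 6.3% | 4.9% |
| 2 | either direction | 9.75% | 9.1% | 7.8% |
| 3 | either direction | 14.3% | 12.5% | 9.8% |

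**If all outcomes must succeed.** A false overall claim requires a false rejection on at least one truly null outcome together with success on all the others, so its probability is at most 5%. Power pays for this: with 80% on each of k independent outcomes, joint power is 0.8² = 64% or 0.8³ = 51%, and it cannot exceed 80% at any correlation.

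**What sidedness is worth.** For the same test and effect, 80% power at one-sided 5% becomes Φ(1.645 + 0.842 − 1.960) = Φ(0.527) ≈ 70% at two-sided 5%. Holding 80% would need (1.960 + 0.842)² / (1.645 + 0.842)² ≈ 1.27 times the subjects.

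**The case against.** The strongest defence is that the plan does state its error rate and direction. One-sided 5% is written in the power sentence with its reason beside it, and Aim 3 is directional, so *different* may just be loose wording. This largely stands. A reader might infer that the plan gives no sidedness at all, and the text does not support that. What remains is narrower: the objective and the test sentence do not match the power sentence.

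Second, the inflation follows only if one success is enough. Hypothesis 3 joins its three outcomes with *and*; read as a requirement for all of them, it produces no inflation. This also stands, and it means that inflation is conditional rather than established. It does not rescue the plan, because Section 8.0 uses *or* and no rule chooses between the two.

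Third, T2, lymphangiography score and PSFS are named in Section 8.0 and could be taken as the intended endpoints. They appear only as the basis for power and are not ranked, so they indicate candidates without settling which is primary.

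Fourth, Section 5.0 (item 8) calls the work a pilot study, and strict alpha control matters less in a small mechanistic imaging study. That is fair as to the choice of adjustment. It does not remove the need to name one primary endpoint when a primary objective, a power and a type I error are all declared.

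Finally, a reader might infer that the 80% is wrong or the trial underpowered. The documents do not support this. Text was removed before review and the preliminary-data sentence may be damaged, so the absent sample size and SD cannot be held against the plan. The undefined effect is a fault in the visible sentence, and it makes the 80% uncheckable, not false.

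**Conclusion.** The point holds in conditional form and should be corrected. The visible plan has no primary endpoint, success rule, testing order or alpha control for Aim 3. If any single success meets the objective, the stated one-sided 5% becomes 7.5% to 9.75% for two outcomes or 9.3% to 14.3% for three, given the assumed number of outcomes and correlations from 0.8 to 0. More outcomes would raise it. If all must succeed, error is controlled and the cost is power. The sidedness mismatch and the undefined 40% are defects of specification, and no claim that the power is too low follows from them.

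One separate contradiction bears on how the paired comparison is read but adds nothing to the multiplicity figures. Section 5.0, item 5, says "For Group 1, the first course of treatment will be CDT alone" and also "For Group 2, the first course of treatment will be CDT alone", with the same second course for both. If that is literal, treatment is confounded with period. It also conflicts with the cross-over design in Section 2.0 and with the treatment-period model in Section 8.0.

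**What to change.** 1. Name one primary endpoint for Aim 3, either PSFS or one named MRI metric. Make the other Hypothesis 3 outcomes secondary, tested in a fixed order or by Holm once the primary has succeeded. Place UEFI in that list or call it exploratory.
2. Use one sidedness in the objective, the tests and the power. Either keep one-sided 5% and word the objective directionally, in line with Aim 3, or move to two-sided 5% and restate the power.
3. Replace the 40% reduction rate with a paired between-therapy difference in change on the named endpoint. Restate power for it at the existing sample size, with that number and the SD shown. Do not carry the 80% over without the calculation.
4. Separately, reconcile the group sequences in Section 5.0 with the cross-over design and the treatment-period model.

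Cost: SAP wording and one power calculation. Outcomes not chosen become secondary, and the stated power may be lower. No extra patients are needed if one-sided 5% is kept or the fall to about 70% under two-sided 5% is accepted. Holding 80% at two-sided 5% would need about 27% more subjects.
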